3.1.4 Internal Monitoring Committee

An IMC will monitor patient safety throughout the study. The IMC will include the Sponsor representatives from Clinical Science, Drug Safety, Biostatistics, and Statistical Programming and Analysis. In addition to the ongoing assessment of the incidence and nature of adverse events (particularly, Grade ≥ 3 events), serious adverse events, deaths, and laboratory abnormalities performed by the investigator and the Medical Monitor, the IMC will review data supporting the determination of the RP2D and cumulative data at regular intervals, every 4 months for safety and efficacy, and ad-hoc if safety concerns arise between the planned regular 4-month intervals, during the expansion phase.

Predefined stopping rules for excess toxicity, including fatal adverse events, have been included in Section 6.11. In the event that any of the stopping rules criteria are met at any time during the course of the study, enrollment of patients will be paused while an IMC meeting is immediately convened to review and provide a recommendation on further conduct of the study (e.g., consider study discontinuation).

At the time of each review, the IMC will make appropriate recommendations (e.g., the study should continue as planned, additional analyses should be performed, enrollment should be held pending further safety evaluations).

Decisions will be made in consideration of the totality of the available data. Ad hoc meetings may be called in addition to scheduled meetings, as necessary, to provide recommendations on management of any potential new safety signals. At the time when all patients have completed or discontinued the maintenance treatment, regular IMC assessments will no longer take place. Ad hoc meetings may be called at the discretion of the Medical Monitor in case of newly identified safety signals. Specific operational details such as the committee's composition, frequency and timing of meetings, members' roles and responsibilities, and data to be reviewed will be detailed in an IMC charter.

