6.11 STOPPING RULES FOR SAFETY

In the event that any of the following criteria are met at any time in the course of the study, the IMC will be immediately convened to review and provide a recommendation for further conduct of the study:

- Fatal adverse events $\geq 10\%$
- Grade 3–4 adverse events $\geq 75\%$

The fatal adverse event threshold of 10% is derived from the completed GADOLIN study (Sehn et al. 2015) and the ongoing external study GALEN (Morschhauser et al. 2017), in which the occurrence rates of Grade 5 adverse events were 6% and 3.4%, respectively. Based on these two studies, the assumed historical control fatal adverse event rate is 5%, and with a 5% addition as a trigger for IMC review, a threshold rate of 10% is used for the stopping rules. The fatal adverse events will be continuously monitored during the conduct of the study and if the number of fatal adverse events reach the pre-specified threshold, the IMC will be immediately convened to decide whether to continue or stop the study (see [Table 15](#)). For each of these incidence rates, the minimized false positive probabilities and the true positive probability of correctly triggering an IMC safety review when the observed fatal adverse event rates are 5% higher than the historical control rate are presented.

Table 15 Early Stopping Rules Based on Number of Fatal Adverse Events

Interim look, n	# (rate, %) of fatal (Grade 5) AE(s) required for an IMC review	Probability of early stopping ^a	
		Probability of correct stop if true experimental regimen fatal AE rate =10% (historical control rate + 5%)	Probability of incorrect stop if true experimental regimen fatal AE rate =5%
27–30	2 (7%)	59%	19%
31–40	2 (5%)	78%	32%
41–45	3 (7%)	67%	19%

AE=adverse event; IMC=Internal Monitoring Committee.

Note: The assumed historical control fatal adverse event rate is 5%.

^a Assessed for upper limit of the interim look sample size (i.e., for n=30, 40, 45).

In addition to fatal adverse events, Grade 3/4 adverse events, which represent severe non-fatal events, will be closely monitored. The threshold of 75% for Grade 3/4 adverse events is derived from the external study GALEN (Morschhauser et al. 2017) and the completed study GADOLIN (Sehn et al. 2015), where the occurrence rates of Grade 3/4 adverse events were 57% and 62%, respectively.

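### Table 15's 41–45 row gives a single-look probability for a continuously monitored rule, so it understates the chance of having triggered an IMC review by n=45 by at least 14 points (true 5%) and about 12 points (true 10%), and no overall rate is given

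*Combined protocol and SAP*

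**What the plan says.** Section 6.11 sets a trigger that applies throughout the study: "The fatal adverse events will be continuously monitored during the conduct of the study". Once the count gets to the threshold, the committee is called at once. Under Section 3.1.4, when a criterion is met, "enrollment of patients will be paused while an IMC meeting is immediately convened"; Section 3.1.3 says the same for the expansion phase. The committee then recommends whether and how the study goes on.

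Table 15 has three bands. It prints 2 fatal events for n=27–30, 2 for n=31–40 and 3 for n=41–45. Under a column heading that speaks of early stopping it gives 59%, 78% and 67% for a true fatal rate of 10%, and 19%, 32% and 19% for a true rate of 5%. Footnote a gives the basis: "Assessed for upper limit of the interim look sample size (i.e., for n=30, 40, 45"). No cumulative or overall probability appears. The same section also lists fatal events in 10% or more of patients, at any time, as a criterion for convening the IMC.

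**The concern.** The bands are met in sequence. A trial enters the 41–45 band only after passing through the first two, and its death count cannot drop on the way. The probability of having triggered by n=45 must therefore be at least the probability of having triggered by n=40. The printed figures go the other way, from 32% to 19% and from 78% to 67%, so the last row cannot describe the rule as it is run.

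This is the trial's predefined rule for fatal events. Someone planning IMC workload, or judging how well the rule protects patients, would naturally take 19% as the false-alarm rate and 67% as the detection rate near full enrolment. The last band is also shown as a working boundary on a par with the others. Because the trigger count loosens at n=41, almost every trial that meets it has already been referred to the IMC.

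**Working it through.** **Inputs (Section 6.11 and Table 15).** Reference rate: "the assumed historical control fatal adverse event rate is 5"%. Alternative: 10%. Evaluation points: n = 30, 40, 45. Printed counts: 2, 2, 3. The text says that reaching the threshold triggers review, so the event is X ≥ r.

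**Step 1: reproduce the printed percentages.** The single-look probability is P(X ≥ r) with X ~ Bin(n, p).

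| n | Printed (10% / 5%) | Printed count, X ≥ r | One more death, X ≥ r+1 |
|---|---|---|---|
| 30 | 59 / 19 | r=2: 81.6 / 44.7 | 3: 58.9 / 18.8 |
| 40 | 78 / 32 | r=2: 92.0 / 60.1 | 3: 77.7 / 32.3 |
| 45 | 67 / 19 | r=3: 84.1 / 39.2 | 4: 67.1 / 18.7 |

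All six printed percentages are single-look tails for 3, 3 and 4 deaths. None matches the printed counts. That mismatch is a separate fault, so both sets of counts are carried forward.

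**Step 2: accumulate over the bands.** Within a band the threshold is constant and the count cannot fall, so checking at every patient is the same as checking at the band's upper n. The first two bands share a threshold, so having triggered by n=40 means X40 ≥ k2. With k3 the threshold in the last band:

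P(triggered by 45) = P(X40 ≥ k2) + Σ over x < k2 of P(X40 = x) × P(Bin(5, p) ≥ k3 − x)

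Counts 3/3/4 (k2 = 3, k3 = 4; terms in the order x = 0, 1, 2):
- p = 0.05: 0.3233 + 0.1285×0.00003 + 0.2706×0.00116 + 0.2777×0.02259 = 0.3299
- p = 0.10: 0.7772 + 0.0148×0.00046 + 0.0657×0.00856 + 0.1423×0.08146 = 0.7894

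Counts 2/2/3 (k2 = 2, k3 = 3; terms in the order x = 0, 1):
- p = 0.05: 0.6009 + 0.0063 = 0.6072
- p = 0.10: 0.9195 + 0.0055 = 0.9250

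An exact patient-by-patient recursion gives the same values whether looks are at every n from 27 to 45 or only at 30, 40 and 45.

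**Step 3: compare the last row with print.**

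| Counts | True rate | Printed | By n=45 | Gap (points) | New first triggers in 41–45 |
|---|---|---|---|---|---|
| 3/3/4 | 5% | 19 | 33.0 | 14.0 | 0.7% |
| 3/3/4 | 10% | 67 | 78.9 | 11.9 | 1.2% |
| 2/2/3 | 5% | 19 | 60.7 | 41.7 | 0.6% |
| 2/2/3 | 10% | 67 | 92.5 | 25.5 | 0.6% |

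The 2/2/3 gaps have two sources. At 5%, 39.2 − 19 = 20.2 points come from the one-death mismatch and 60.7 − 39.2 = 21.5 from accumulation. At 10%, the split is 84.1 − 67 = 17.1 and 92.5 − 84.1 = 8.4.

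**Step 4: add the 10% criterion.** Read literally from the first patient, review is also due whenever deaths/n ≥ 10%. Running the recursion with whichever threshold is lower at each n gives 53.3% (true 5%) and 87.1% (true 10%) by n=45 with 3/3/4, and 67.3% and 94.0% with 2/2/3.

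**The case against.** The strongest reply is that the table never claims to be cumulative. Footnote a states the single sample size behind each row, and the six percentages are correct tails for 3, 3 and 4 deaths. That stands. The fault is an operating characteristic left out under a misleading column heading; the sums themselves are not wrong. A reader might infer that every row is wrong for want of accumulation. The documents do not support that, because rows 1 and 2 share a threshold and their single-look values already equal the cumulative ones for the same count. They change only if the count mismatch is resolved in favour of the printed counts.

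Second, crossing a threshold convenes the IMC and does not end the trial. A reader might infer that a third or more of acceptable trials would be wrongly stopped. The documents do not say that, since the committee may let the study continue. The last band could then serve as a further review. This does not rescue 19% as printed. With 3/3/4 at a true 5%, the chance of meeting the last band is about 1% with no trigger by n=40 and about 56% after one. The printed figure averages the two (0.677×0.0097 + 0.323×0.557 ≈ 0.187) and describes neither situation.

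Third, the practical harm is bounded: a false trigger costs a pause and a meeting, and the IMC reviews safety every 4 months anyway. That limits the weight of the point without removing it.

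**Conclusion.** The point holds for the 41–45 row. Whichever count is in force, that row understates the probability of having triggered an IMC review by n=45: by at least 14 points at a true 5% rate and by about 12 or more at a true 10% rate. The 14 and 12 belong to 3/3/4, the counts that reproduce the percentages. The counts actually printed give about 42 and 26, but it would be wrong to put all of that down to sequential monitoring, since a good part is the one-death mismatch. The row contributes a first trigger in only about 0.6–1.2% of trials, and no overall error rate is stated.

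The figures assume that patients counted in n are fully observed and that deaths are independent with a constant rate. They cover Table 15's bands alone. If the 10% criterion also applies from the first patient, the overall figures are higher (about 53% and 87% with 3/3/4, about 67% and 94% with 2/2/3). For that reason 33% and 79% should not simply be copied in as the overall rate. This is a correction to how the safety rule is described; it does not show which threshold is right.

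**What to change.** First reconcile three things in Section 6.11 that do not agree: the count column, the percentages, and the criterion of 10% or more at any time. The choice of threshold is the sponsor's.

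Then, in Table 15, print the cumulative probability of having triggered an IMC review by n=30, 40 and 45 under the full rule in force, with one overall line. Head the columns as probability of IMC review, not of stopping. For Table 15's bands alone, the entries at 5% would be 18.8, 32.3 and 33.0% and at 10% 58.9, 77.7 and 78.9% for 3/3/4. For 2/2/3 they would be 44.7, 60.1 and 60.7% and 81.6, 92.0 and 92.5%. If the 41–45 row is meant as a further review after an earlier one, label it so and say what its probability is conditional on.

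The cost is one table and a sentence or two, with no extra patients or data. The drawback is that the stated false-trigger rate becomes less favourable.

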3.1.3 Expansion Phase

The expansion phase is designed to further assess the safety and efficacy of the combination of atezolizumab with obinutuzumab plus lenalidomide when given as induction and maintenance treatment.

Approximately 40 patients with FL will be enrolled during the expansion phase and treated as described below. Patients who received lenalidomide at the RP2D during the dose-escalation phase will be pooled with patients treated in the expansion phase. All patients will receive induction treatment as outlined in [Table 2](#).

Table 2 Induction Treatment for Expansion Phase

Cycle(s)	Atezo + G + Len (28-Day Cycles)
1	
 • Lenalidomide at RP2D PO once daily on Days 1–21 • Obinutuzumab 1000 mg IV on Days 1, 8, and 15
2–6	
 • Lenalidomide at RP2D PO once daily on Days 1–21 • Obinutuzumab 1000 mg IV on Day 1 • Atezolizumab 840 mg IV on Days 1 and 15

IV=intravenous; PO=by mouth; RP2D=recommended Phase II dose.

Patients who achieve a CR, a PR, or stable disease at EOI will receive maintenance treatment with Atezo + G + Len, as outlined in [Table 3](#). Maintenance treatment should start 8 weeks (\pm 1 week) after Day 1 of Cycle 6 and will continue until disease progression or unacceptable toxicity for up to 24 months.

Table 3 Maintenance Treatment

Patients with FL	
Maintenance treatment consisting of the following, administered for 24 months (from Months 1–24 ^a):
 
 • Lenalidomide 10 mg PO once daily on Days 1–21 of each month for a maximum of 12 months • Obinutuzumab 1000 mg IV on Day 1 of every other month (i.e., every 2 months), starting with Month 1 • Atezolizumab 840 mg IV on Days 1 and 2 of each month
------------------	---

[figure not shown]
FL=follicular lymphoma; IV=intravenous; PO=by mouth.

^a 1 month=28 days.

In the event that any one of the stopping rules criteria (refer to [Section 6.11](#) for further details) occurs at any time in the expansion phase, enrollment of patients will be paused while an IMC is immediately convened to review and provide a recommendation on further conduct of the study (e.g., consider study discontinuation).

A schedule of assessments is provided in [Appendix 1](#), and a study schema is provided in [Figure 1](#).

Figure 1 Study Schema

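### Table 15's fatal-event counts, its stop probabilities and the 10% trigger in Section 6.11 describe different rules; counts and probabilities are one death apart in every row

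*Combined protocol and SAP*

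**What the plan says.** Section 6.11 lists fatal adverse events of 10% or more as a criterion for convening the IMC at once. It derives this by adding 5 percentage points to an assumed historical rate of 5%, and states that "a threshold rate of 10% is used for the stopping rules". It then points to Table 15 for the operating rule: "The fatal adverse events will be continuously monitored during the conduct of the study", and the IMC meets "if the number of fatal adverse events reach the pre-specified threshold".

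The count column of Table 15 is headed "rate, %) of fatal (Grade 5) AE(s) required for an IMC review". Its three rows are:

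- n=27–30: 2 deaths (7%), correct stop 59%, incorrect stop 19%
- n=31–40: 2 deaths (5%), correct stop 78%, incorrect stop 32%
- n=41–45: 3 deaths (7%), correct stop 67%, incorrect stop 19%

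Correct stop is evaluated at a true fatal-event rate of 10%, incorrect stop at 5%. Footnote a gives the basis of the probabilities: "Assessed for upper limit of the interim look sample size", that is n=30, 40 and 45.

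On the consequence, Section 3.1.4 says that "enrollment of patients will be paused while an IMC meeting is immediately convened", and Section 3.1.3 says the same for the expansion phase. Section 3.1.4 adds: "Decisions will be made in consideration of the totality of the available data".

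**The concern.** The heading speaks of deaths required and the text of deaths reaching a threshold. Both mean at least the printed number, yet the printed probabilities look too low for at least 2 deaths in 30 or 40 patients. The printed rates of 7%, 5% and 7% are also all below the 10% that the table is meant to put into effect, and the middle one equals the assumed historical rate.

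Two things are at stake. First, the error rates quoted for a mortality rule may not be those of the rule that will be applied. Second, someone monitoring deaths cannot tell from Section 6.11 whether the rule has been met: with 2 or 3 deaths in 40 patients, the table calls for a review and the 10% criterion does not.

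**Working it through.** **Inputs**, all from Section 6.11 and Table 15: n = 30, 40, 45 (footnote a); true rates p = 0.10 and 0.05; counts r = 2, 2, 3; criterion of 10% or more.

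**Formula.** With X deaths among n patients, X ~ Binomial(n, p), the single-look trigger probability is P(X ≥ r) = 1 − Σ_{k<r} C(n,k) p^k (1−p)^(n−k).

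**Worked row, n=30.** At p=0.10, P(0)=0.0424, P(1)=0.1413 and P(2)=0.2277.

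- At least 2: 1 − 0.0424 − 0.1413 = 0.8163
- At least 3: 0.8163 − 0.2277 = 0.5886, the printed 59%

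At p=0.05, the terms are 0.2146, 0.3389 and 0.2586.

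- At least 2: 1 − 0.2146 − 0.3389 = 0.4465
- At least 3: 0.4465 − 0.2586 = 0.188, the printed 19%

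**All rows** (percent, true rate 10% / 5%):

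| n | Table 15 prints | Printed count (2, 2, 3) | One more death (3, 3, 4) | Smallest count at ≥10% (3, 4, 5) |
|---|---|---|---|---|
| 30 | 59 / 19 | 81.6 / 44.6 | 58.9 / 18.8 | 58.9 / 18.8 |
| 40 | 78 / 32 | 92.0 / 60.1 | 77.7 / 32.3 | 57.7 / 13.8 |
| 45 | 67 / 19 | 84.1 / 39.2 | 67.1 / 18.7 | 47.3 / 7.3 |

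All six printed probabilities match the one-more-death column to the whole percent, and none matches the printed counts. With the counts read as at least, using the lower end of each n range, a Poisson tail or cumulative crossing does not reproduce any row either.

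**Are the count digits misread?** No. 2/30 = 6.7%, 2/40 = 5.0% and 3/45 = 6.7% are the printed 7%, 5% and 7%. Counts of 3, 3 and 4 would have shown 10.0%, 7.5% and 8.9%.

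**Against the 10% criterion, over each n range:**

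- Printed counts: 2/27 to 2/30 = 7.4 to 6.7%; 2/31 to 2/40 = 6.5 to 5.0%; 3/41 to 3/45 = 7.3 to 6.7%. All are below 10%.
- One more death: 3/27 to 3/30 = 11.1 to 10.0%, which meets it; 3/31 to 3/40 = 9.7 to 7.5% and 4/41 to 4/45 = 9.8 to 8.9%, which do not.

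Row 1's probabilities therefore agree with the 10% criterion and only its count differs. In rows 2 and 3 the count, the probabilities and the criterion give three different rules.

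**Size of the gap.** False-trigger chance at a true 5% rate, printed counts against stated: 45/19 = 2.4, 60/32 = 1.9, 39/19 = 2.1.

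**Secondary: cumulative crossing probability up to n=45**, by patient-by-patient recursion (true rate 10% / 5%):

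- 2/2/3 from n=27: 92.5 / 60.7%
- 3/3/4 from n=27: 78.9 / 33.0%
- ≥10% from n=27: 67.0 / 21.7%; from n=20: 74.0 / 31.9%; from the first patient: 81.9 / 48.5%

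The starts at n=20 and at the first patient are assumptions made here to show the range; Table 15 begins at n=27.

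**The case against.** The best counter-argument is that a greater-than sign was lost before 2, 2 and 3, in the source or when the PDF was read. The same document shows an apparent loss of this kind in Section 3.3.2.3, where a p-value appears as p0.0001. More than 2, 2 and 3 deaths would carry the same bracketed percentages and would make every printed probability correct. This cannot be excluded, so the 45/60/39% figures hold only if the counts are as read. Against it, neither the heading nor the text says more than. It also would not repair the section, because 3/40 = 7.5% and 4/45 = 8.9% would still fall short of the 10% criterion.

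It can also be said that both triggers lead to the same action, so the earlier one could simply operate. But Section 6.11 presents Table 15 as the way the 10% threshold is applied, not as a second rule.

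On consequences, much of the defence stands. A trigger is not a termination. The printed counts err toward earlier review, so they do not leave patients less protected. The IMC also reviews cumulative data every 4 months and follows deaths from all causes, and the primary response estimate is unaffected. Footnote a discloses the single-look basis, so the cumulative figures are an addition and not a further error.

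**Conclusion.** The concern holds. As written, Table 15's probabilities are those of a rule requiring one more death than the counts printed beside them, in all three rows. The counts are below the 10% trigger throughout.

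If the counts are as read, stated false-trigger chances of 19, 32 and 19% become 45, 60 and 39%, and enrollment would be paused more often than stated at the assumed historical 5% rate. If the 10% criterion is the operative rule, the chance of triggering at a true 10% rate is 58% at n=40 (stated 78%) and 47% at n=45 (stated 67%). If a greater-than sign was lost, the stated probabilities are right but rows 2 and 3 still contradict the 10% criterion. No reading makes the section consistent.

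The figures assume independent patients with a common fatal-event rate and a single look at the top of each n range, as footnote a specifies. The correction is needed because the rule pauses enrollment over deaths and must be unambiguous.

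**What to change.** The sponsor should reconcile the 10% text, the Table 15 counts and the Table 15 probabilities into one trigger, state it explicitly as at least or more than, and print the probabilities that go with it. This review does not choose among them. The matching single-look values at n=30, 40 and 45 (true rate 10% / 5%) are:

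- at least 2, 2, 3 deaths: 82/45, 92/60, 84/39%
- at least 3, 3, 4 deaths: 59/19, 78/32, 67/19%
- at least 3, 4, 5 deaths (10% or more): 59/19, 58/14, 47/7%

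Because deaths are monitored continuously, it would help to add the cumulative trigger probability, with the patient number at which monitoring starts. The scope should be aligned in the same edit: Section 3.1.3 ties the rule to the expansion phase, whereas Sections 3.1.4 and 6.11 apply it throughout the study.

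The cost is a text and table correction, carried into the IMC charter, and a few lines of code. No patients, visits or procedures are added. The sponsor would have to accept less favorable stated figures in two cases: higher false-trigger rates if 2/2/3 is confirmed, or lower detection at n=40 and n=45 if 10% is confirmed.

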7. DATA COLLECTION AND MANAGEMENT

7.1 DATA QUALITY ASSURANCE

The Sponsor will be responsible for data management of this study, including quality checking of the data. Data entered manually will be collected via EDC through use of eCRFs. Sites will be responsible for data entry into the EDC system. In the event of discrepant data, the Sponsor will request data clarification from the sites, which the sites will resolve electronically in the EDC system.

The Sponsor will produce an EDC Study Specification document that describes the quality checking to be performed on the data. Central laboratory data and any other externally-generated electronic study data will be sent directly to the Sponsor, using the Sponsor's standard procedures to handle and process the electronic transfer of these data.

eCRFs and correction documentation will be maintained in the EDC system's audit trail. System backups for data stored by the Sponsor and records retention for the study data will be consistent with the Sponsor's standard procedures.

